### 8.3.2. Pregnancy

#### Collection of pregnancy information

##### *Male participants with partners who become pregnant*

- The investigator will attempt to collect pregnancy information on any male participant's female partner who becomes pregnant while the male participant is in this study. This applies only to male participants who receive study intervention.

- After learning of a pregnancy in the female partner of a study participant, the investigator
  - will request a consent or assent to release information from the pregnant female partner directly, and
  - within 24 hours after obtaining this consent or assent, will record pregnancy information on the appropriate form and submit it to the sponsor.

The female partner will also be followed to determine the outcome of the pregnancy. Information on the status of the mother and child will be forwarded to the sponsor. Generally, the follow-up will be no longer than 6 to 8 weeks following the estimated delivery date. Any termination of the pregnancy will be reported regardless of gestational age, fetal status (presence or absence of anomalies), or indication for the procedure.

#### ***Female participants who become pregnant***

- The investigator will collect pregnancy information on any female participant who becomes pregnant while participating in this study. The initial information will be recorded on the appropriate form and submitted to the sponsor within 24 hours of learning of a participant's pregnancy.
- The participant will be followed to determine the outcome of the pregnancy. The investigator will collect follow-up information on the participant and the neonate and the information will be forwarded to the sponsor. Generally, follow-up will not be required for longer than 6 to 8 weeks beyond the estimated delivery date. Any termination of pregnancy will be reported, regardless of gestational age, fetal status (presence or absence of anomalies) or indication for the procedure.
- While pregnancy itself is not considered to be an AE or SAE, any pregnancy complication or elective termination of a pregnancy for medical reasons will be reported as an AE or SAE.
- A spontaneous abortion (occurring at <20 weeks gestational age) or still birth (occurring at ≥20 weeks gestational age) is always considered to be an SAE and will be reported as such.
- Any post-study pregnancy related SAE considered reasonably related to the study intervention by the investigator will be reported to the sponsor as described in protocol Section 8.3.1. While the investigator is not obligated to actively seek this information in former study participants, he or she may learn of an SAE through spontaneous reporting.
- Any female participant who becomes pregnant while participating in the study will discontinue study intervention. If the participant is discontinued from the study, follow the standard discontinuation process and continue directly to the follow-up phase. The follow-up on the pregnancy outcome should continue independent of intervention or study discontinuation.

Prior to continuation of study intervention following pregnancy, the following must occur:

- The sponsor and the relevant institutional review board/independent ethics committee (IRB/IEC) give written approval.
- The participant gives signed informed consent (and assent, as applicable).
- The investigator agrees to monitor the outcome of the pregnancy and the status of the participant and the participant's offspring.

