### 7.1. Discontinuation of Study Intervention

When necessary, a participant may be permanently discontinued from study intervention. If so, the participant will remain in the study to complete procedures for an early discontinuation visit and post-treatment follow-up, if applicable, as shown in the SoA.

A participant should be permanently discontinued from study intervention if

- the participant becomes pregnant during the study
- in the opinion of the investigator, the participant should permanently discontinue the study intervention for safety reasons
- the participant develops a malignancy, except for successfully treated basal or squamous cell skin carcinoma
- the participant tests positive for HBV DNA (see Section 8.2.3)
- the participant tests positive for HCV RNA (Section 8.2.4)
- if the participant experiences a hepatic event or liver test abnormality as specified in the liver chemistry stopping criteria (see Section 7.1.1)
- the participant develops HIV infection
- the participant develops any infection that is opportunistic, such as active tuberculosis and other infections whose nature or course may suggest an immuno-compromised status
- the participant requires rescue medication treatment for symptoms of AD in the treatment period, and
- the participant has an AE or an SAE or a clinically significant change in a laboratory value that, in the opinion of the investigator, merits discontinuation of study intervention and appropriate measures being taken.

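### Protocol Sections 7.1 and 8.3.2 agree that study drug stops when a participant becomes pregnant, but conflict on whether it may ever resume

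*Protocol*

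**What the plan says.** Protocol Section 7.1 opens its list of stopping reasons with "A participant should be permanently discontinued from study intervention if", and the first item is that "the participant becomes pregnant during the study". No exception is attached. For anyone stopped under this section, "the participant will remain in the study to complete procedures for an early discontinuation visit and post-treatment follow-up", if applicable. No return to dosing is described there for pregnancy.

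Protocol Section 8.3.2, under the heading for female participants who become pregnant, begins the same way: "Any female participant who becomes pregnant while participating in the study will discontinue study intervention". The same subsection then ends with a block introduced by "Prior to continuation of study intervention following pregnancy, the following must occur". Three conditions follow:

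- "The sponsor and the relevant institutional review board/independent ethics committee (IRB/IEC) give written approval".
- The participant signs consent, with assent where that applies.
- "The investigator agrees to monitor the outcome of the pregnancy and the status of the participant and the participant's offspring".

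**The concern.** The two sections give different answers to one practical question: once study drug has been stopped for pregnancy, is that final? A site that consults Section 7.1 finds a permanent stop. A site that consults Section 8.3.2 finds a list of steps to complete before dosing continues. Neither section mentions the other.

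The continuation block is also unclear about its own timing. The words *following pregnancy* can mean after the participant has become pregnant, or after the pregnancy has ended. The third condition looks forward to the outcome of the pregnancy, so the first meaning cannot be ruled out.

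The protocol otherwise takes care to avoid exposure in pregnancy. Exclusion 44 bars pregnant or breastfeeding participants. Inclusion criterion 10 requires contraception or abstinence during treatment and for at least 18 weeks after the last dose. The Schedule of Activities repeats urine tests through the treatment period. An unresolved instruction about re-dosing sits badly with those provisions, and enrolment starts at age 12.

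**Working it through.** The point is textual. There is no planned figure to reproduce. The check sets the sections side by side and looks for anything that reconciles them.

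**1. At the moment pregnancy is found.** Section 7.1: stop. Section 8.3.2: stop. They agree.

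**2. Afterwards.** Section 7.1: the stop is permanent and leads to an early discontinuation visit and post-treatment follow-up. Section 8.3.2: continuation is foreseen if three conditions are met. Both cannot hold for the same participant.

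**3. Is there a bridge elsewhere?**

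- Section 7.1.2 (temporary discontinuation) covers serious or opportunistic infection, HBV DNA detected below the level of quantification, and weight loss below 40 kg in participants under 18. Pregnancy is not there.
- Section 7.1.1 does provide for resuming study drug, but only for liver tests, and the liver item in Section 7.1 points to it. The pregnancy item in Section 7.1 points nowhere.
- No sentence gives Section 8.3.2 precedence over Section 7.1.

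**4. When could the continuation block operate?** The synopsis gives up to 24 weeks of treatment, and the dosing table puts the last scheduled dose at Week 20 (Q4W) or Week 22 (Q2W).

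- A pregnancy that begins on or after the first dose would have to end in less than 22 weeks for a scheduled dose to remain within the Treatment Period.
- As a reference, assume a full-term pregnancy of about 40 weeks (not given in the documents). A term delivery before the last scheduled dose would then require a participant already 40 − 22 = 18 weeks pregnant at first dose. With serum testing at screening and urine testing at baseline, that should not occur.
- So within the 24-week Treatment Period the block could apply only during a pregnancy or after one that ended before term.
- That limit does not extend beyond Week 24. Protocol Section 6.6 and SAP Section 4.1 describe a Continued Access Period under Protocol Addendum 3. The addendum is not among the documents, so whether Section 8.3.2 applies in that period cannot be settled here.

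**5. Does either reading of the timing remove the conflict?** If the clause means during pregnancy, it conflicts with a permanent stop. If it means after pregnancy, it still conflicts with a permanent stop. The ambiguity is a second defect; it does not resolve the first.

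**The case against.** **Section 7.1 says should, not must.** On this view it sets a default, and Section 8.3.2 supplies a specific exception with safeguards. The protocol does use *must* in places, for example for rescue therapy in Section 6.8.4. But every reason in Section 7.1 shares the same opening, including malignancy and HIV infection. Section 7.1.2 refers to Section 7.1 as the source of a mandatory permanent stop for confirmed HBV DNA. The wording therefore does not mark pregnancy as a softer rule.

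**The safeguards are real.** Section 8.3.2 orders no dosing. A site cannot restart alone: the sponsor and the ethics committee must approve in writing and the participant must consent. This stands. A reader might infer that following Section 8.3.2 would by itself re-expose a pregnant participant, or that every positive test meets contradictory instructions. The text does not support that, because both sections say to stop and the conflict appears only when continuation is later sought.

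**Following pregnancy may mean after it ends.** That is a fair reading, and follow-up of the participant and offspring fits it. A reader might infer that the protocol provides for dosing while the outcome is unknown. That is an inference from an ambiguous phrase, not a stated provision.

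**The clause may serve Continued Access.** Possibly, but Section 8.3.2 does not say so. The SAP schema notes say Continued Access treatment ends when criteria for discontinuing study intervention are met. If those criteria are the ones in Section 7.1, the same conflict would arise there.

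**Conclusion.** The inconsistency is real and narrow. Sections 7.1 and 8.3.2 agree on stopping and disagree on whether dosing may ever resume, and the continuation block does not state its timing or study period. It touches only a participant who becomes pregnant and for whom continuation is then sought. The documents give no expected number; exclusion 44, contraception and repeated testing should keep it small. It would be too much to say that it affects every participant of child-bearing potential.

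A reader might also infer a consequence for the primary estimand, which is limited to participants who remain on treatment until Week 16. The documents do not support a material effect. The analysis is descriptive and uses observed data. How to classify someone who stops and restarts is a general question that arises equally for infection withholding and liver interruption.

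The conclusion rests on the two sections as written and on finding no reconciling text in the protocol or SAP. It does not depend on the 40-week assumption, and it takes no view on which rule is right. It merits correction because two stopping instructions that bear on participant safety should not differ, and correcting them is cheap.

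**What to change.** The sponsor should decide which rule is intended and reconcile Sections 7.1 and 8.3.2 so that one instruction governs whether study intervention may resume after a pregnancy.

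- If the Section 7.1 text is to govern, remove or reword the continuation block in Section 8.3.2.
- If a continuation clause is to be kept, qualify the pregnancy item in Section 7.1, state whether the clause applies during a pregnancy or only after it has ended, and name the study period in which it operates (Treatment Period, Continued Access, or both).
- In either case, cross-reference the two sections and check that Protocol Addendum 3 says the same.

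The cost is one text edit at the next amendment and a notice to sites. No procedures, visits or analyses are added.

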### **8.3.3. Adverse Events of Special Interest**

The following TEAEs will be designated AE of special interest (AESI):

- conjunctivitis
- herpes infection or zoster, and
- parasitic infection or an infection related to an intracellular pathogen.

If these AESIs are reported, sites will be prompted to collect additional data. Participant records must include any follow-up information regarding these AESI. Study intervention should be discontinued if an AE is deemed persistent and if continuation of study intervention would not be in the best interest of the participant. Discuss discontinuation of study intervention with the sponsor or designee prior to implementation.

#### **8.3.3.1. Infections, Including Serious Infections and Opportunistic Infections**

Completion of the Infection CRF page is required for each infection reported as an AE or SAE. The sponsor will identify infections considered to be opportunistic based on the article by Winthrop et al. (2015) (Section 10.9, Appendix 9).

#### **8.3.4. Facial Dermatitis**

Completion of the facial dermatitis follow-up CRF page is required for each facial dermatitis event reported as an AE or SAE.

#### **8.3.5. Hypersensitivity**

Many drugs, including oral agents and biologic agents, carry the risk of systemic hypersensitivity reactions. If such a reaction occurs, additional data should be provided to the sponsor in the designated CRFs.

Sites should have appropriately trained medical staff and appropriate medical equipment available when study participants are receiving study intervention. It is recommended that participants who experience a systemic hypersensitivity reaction be treated per national and international guidelines.

In the case of a suspected systemic hypersensitivity event, additional blood samples should be collected as described in Section 10.2.1. Laboratory results are provided to the sponsor via the central laboratory.

#### **8.3.6. Injection Site Reactions**

Symptoms and signs of a local injection site reaction may include erythema, induration, pain, pruritus, and edema.

If an injection site reaction is reported by a participant or site staff, the injection site reaction CRF will be used to capture additional information about this reaction (for example, injection-site pain, degree and area of erythema, induration, pruritis, and edema).

#### **8.4. Pharmacokinetics**

At the visits and times specified in the SoA, venous blood samples will be collected and stored for potential analysis of serum concentrations of lebrikizumab.

Samples will be stored at a facility designated by the sponsor and may be assessed at a later date at a laboratory approved by the sponsor using a validated enzyme-linked immunosorbent assay method.

Instructions for the collection and handling of blood samples will be provided by the sponsor. The actual data and time (24-hour clock time) of each sample and the most recent lebrikizumab dose prior to PK blood draw must be recorded.

Sample retention is described in Section 10.1.11. Bioanalytical samples collected to measure investigational product concentrations will be retained for a maximum of 1 year following last participant visit for the study. During this time, samples remaining after the bioanalysis may be used for exploratory analyses such as bioanalytical assay validation or cross-validation exercises.

#### **8.5. Pharmacodynamics**

[figure not shown]
Pharmacodynamic parameters are not evaluated in this study.

#### **8.6. Genetics**

A blood sample for DNA isolation will be collected from participants.

See Section 10.5, Appendix 5 for Information regarding genetic research and Section 10.1.11 for details about sample retention and custody.

#### **8.7. Biomarkers**

- Serum samples will be collected to discern responder variability within the study and to track response variability to lebrikizumab. Biomarkers will include but not limited to   
 Samples will be collected according to the schedule described in the SoA and as detailed in laboratory manual provided separately to sites.
- The sponsor may store samples according to Section 10.1.11. Additionally, with participants' consent, samples may be used for further research by the sponsor or others such as universities or other companies to contribute to the understanding of AD or other diseases, the development of related or new treatments, or research methods.

#### **8.8. Immunogenicity Assessments**

At the visits and times specified in the SoA, venous blood samples will be collected for the purpose of determining antibody production against lebrikizumab. To aid interpretation of these results, a blood sample for PK analysis will be collected at the same time points.

All samples for immunogenicity should be taken pre-dose when applicable and possible. Instructions for the collection and handling of blood samples will be provided by the sponsor. The actual date and time (24-hour clock time) of each sample collection will be recorded. Immunogenicity samples will be stored at a facility designated by the sponsor and may be assessed at a later date using a validated assay designed to detect anti-drug antibodies (ADAs) in the presence of lebrikizumab at a laboratory designated by the sponsor. Samples may also be used for the development and control of an immunogenicity assay.

Treatment-emergent ADAs are defined in Section [9.3.6.4](#).

Sample retention is described in Section [10.1.11](#).

## **8.9. Health Economics**

Health economics and/or medical resource utilization will not be collected as part of this study.

## 9. Statistical Considerations

The SAP will be finalized prior to first patient visit, and it will include a more technical and detailed description of the statistical analyses described in this section. This section is a summary of the planned statistical analyses of the most important endpoints, including primary and key secondary endpoints.

### 9.1. Statistical Hypotheses

The primary objective is to evaluate efficacy of lebrikizumab 250 mg Q2W on reducing skin sign of AD, measured by percentage of patients who achieve at least 75% improvement in baseline EASI at Week 16 in participants with skin of color.

This is an open-label study, no statistical hypothesis will be tested. No inferential statistical analysis will be performed.

### 9.2. Analyses Sets

Participant Analysis Set	Description
ITT population	All enrolled participants. Participants will be included in the analyses according to the planned intervention.
Safety population	All enrolled participants who are exposed to study intervention.

Abbreviation: ITT = intent-to-treat.

## 9.3. Statistical Analyses

### 9.3.1. General Considerations

Statistical analysis of this study will be the responsibility of Eli Lilly and Company (Lilly) or its designee. A detailed SAP describing the statistical methodologies will be developed by Lilly or its designee.

Any change to the data analysis methods described in the protocol will require an amendment ONLY if it changes a principal feature of the protocol. Any other change to the data analysis methods described in the protocol, and the justification for making the change, will be described in the clinical study report (CSR). Additional exploratory analyses of the data will be conducted as deemed appropriate.

All analyses will be descriptive. Frequencies, percentages and 90% confidence interval (CI) for percentages will be reported for discrete efficacy endpoints. Mean, standard deviation, minimum, Q1, median, Q3, maximum, and the number of participants will be reported for continuous efficacy endpoints. AEs, discontinuation, and other categorical safety data will be summarized using frequencies and percentage. Continuous vital signs, body weight, and other continuous safety variables including laboratory variables will be summarized descriptively as well.

### **9.3.2. Primary Endpoint(s)/Estimand(s) Analysis**

The primary endpoint is EASI 75 response rate at Week 16. The primary clinical question of interest is: What is the intervention effect in percentage of participants achieving EASI 75 after 16 weeks of lebrikizumab 250 mg intervention in participants with skin of color and moderate-to-severe AD who remain on study treatment until Week 16. There are no intercurrent events since participants who initiate rescue medication are discontinued from the study and hence study treatment. Therefore, participants who stay on study treatment through Week 16 will not have an intercurrent event such as initiating rescue medication or permanently discontinuing treatment. All observed data will be included in summary statistics. All summary statistics will be based on observed data.

### **9.3.3. Secondary Endpoint(s)/Estimand(s) Analysis**

Secondary endpoints specified in Section 3 will be analyzed similarly to the primary endpoint of the primary estimand, that is, using all observed data.

### **9.3.4. Exploratory Endpoint(s) Analysis**

Other exploratory endpoints specified in Section 3 will be summarized using all observed data.

### **9.3.5. Safety Analyses**

All safety data will be descriptively summarized using the safety population.

TEAEs are defined as AEs that first occurred or worsened in severity after the first dose of study treatment. The number and percentage of participants who experienced at least 1 TEAE will be summarized using the most current version of MedDRA (Medical Dictionary for Regulatory Activities) by system organ class (or body system) and by each preferred term. SAEs and AEs that lead to discontinuation of study intervention will also be summarized.

All clinical laboratory results will be descriptively summarized. Individual results that are outside of normal reference ranges will be flagged in data listings. Quantitative clinical hematology, chemistry, and urinalysis variables obtained at the baseline to postbaseline visits will be summarized as changes from baseline. Categorical variables, including the incidence of abnormal values and incidence of AEs of special interest, will be summarized by frequency and percentage of participants in corresponding categories. Shift tables might be presented for selected measures.

Observed values and changes from baseline (predose or screening if missing) for vital signs and physical characteristics will be descriptively summarized by time point.

The SAP may include additional safety analyses if needed.

### **9.3.6. Other Analyses**

#### **9.3.6.1. Subgroup Analyses**

Subgroup (subpopulation) analyses of the primary and some secondary endpoints at Weeks 16 and 24 may be conducted for intent-to-treat set. Subgroup to be evaluated may include baseline severity, sex, age, race, Fitzpatrick skin type.

Definitions for the levels of the subgroup variables and any additional subgroup analyses will be defined in the SAP. All subgroup analyses will be descriptive and should be treated as exploratory.

